7. SPECIFIC OBJECTIVES OR HYPOTHESES

O1. Evaluate the safety and tolerability of exposure to stroboscopic light in MDD.

O2. Collect critical data on the stroboscopic parameters that reliably elicit tolerable, comfortable and engaging experiences and the (control) parameters that cause minimal stroboscopic experiences.

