10. INCLUSION AND ELIGIBILITY CRITERIA FOR PARTICIPANTS

Inclusion:

- 1. 18 years of age or older.
- 2. Willingness to take part in the study.
- 3. PHQ-9 score indicative of mild to severe depression (score of 5-27).

Exclusion:

1. Positive response to any question on the safety screening protocol (see attached).

2. Currently pregnant.

3. History of or current substance or drug abuse.

4. History of or current diagnosis of psychosis; bipolar disorder; Parkinson's Disease; dementia; Alzheimer's disease.

5. A history of traumatic brain injury (TBI).

6. Presence of certain eye disorders such as retinal blindness, cataracts, retinal diseases of the eye and glaucoma.

A. INTERVENTIONS FOR EACH GROUP WITH SUFFICIENT DETAIL TO ALLOW REPLICATION, INCLUDING HOW AND WHEN THEY WILL BE ADMINISTERED

Within this tolerability study (WP1) we have opted for a single-arm design without a control group, as the primary objective is to assess the intervention's feasibility and tolerability rather than its efficacy. Feasibility studies are typically not designed to test efficacy but to determine whether an intervention can be successfully implemented. In this case, the primary objective is to evaluate tolerability rather than compare outcomes between conditions. In early-phase research, single-arm designs are common, especially when the aim is to gather initial safety and acceptability data before planning a controlled trial. Since this study focuses on participant-reported tolerability and adverse effects, a comparison group is not necessary for this initial evaluation.

Our primary measure of depressive symptomatology is the Patient Health Questionnaire-9 (PHQ-9), with secondary measures including the Maudsley 3-Item Visual Analogue Scale (M3VAS), and Beck's Depression Inventory-II, all of which will be completed by participants before the study (see Figure 1).

Figure 1. Workflow for Work Package 1.

All stroboscopic stimulation will be delivered using a CE-certified commercial stroboscope, roXiva RX1, which consists of 16 LEDs with an overall maximum luminance of 16,000 lux at 0.5 meters. For comparison, light therapy lamps designed to treat Seasonal Affective Disorder (SAD) typically emit 10,000 lux, which is about 10% of the luminance from the sun on a clear day (Campbell et al., 2019); all luminance levels used in this study are well safety guidelines specified by the European Photobiological Safety Directive 2006/25/EC.

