After each 2-minute session, participants will be asked whether they had any side effects; if they select no, they will not be asked any further information regarding the tolerability of the current session. If participants indicate that they experienced adverse effects, they will be presented with a list of symptoms from the Visual Discomfort Questionnaire to select the frequency at which each symptom occurred (Vinkers et al., 2024). Any reported side effect will then be rated on a 10-point scale, this will be referred to as the *tolerability score* or symptom discomfort score, the scale ranges from 0 (no symptom discomfort) to 10 (worst possible symptom discomfort), with 3 indicating mild symptom discomfort, 5 moderate symptom discomfort, and >7 severe symptom discomfort. Any report of a scorer >7 will result in that parameter's testing being stopped immediately to avoid further discomfort.

Participants will also report their overall experience on a 0-100 sliding scale via Qualtrics, asking the participant to report how engaging, pleasurable, overall uncomfortable, and sleepy each session was.

After each round of questions, participants will have an opportunity to share their thoughts on the session and also have a break.

To ensure that the experimental procedure has not inadvertently increased participants' depressive symptoms, participants will fill out the M3VAS change and the PHQ-9 again at the end of the testing session. If participants report a deterioration in well-being as indexed by any increase in M3VAS scores in the pre-to-post measurements, support will be offered and the participant referred to relevant sources of support, such as the University of Sussex-specific counselling services for students, as well as their GP, general non-emergency mental health support, or local A&E services, depending on the severity of symptoms.

After the administration of all sessions and questionnaires, participants will be debriefed; this will be the end of the testing session.

B. CRITERIA FOR DISCONTINUING OR MODIFYING ALLOCATED INTERVENTIONS FOR A GIVEN TRIAL PARTICIPANT

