As this study is collecting preliminary data to inform the development of a stroboscopic intervention in WP2, we will not be discontinuing the intervention unless requested to by the participant;however, in the case of the current experiment if participants report a tolerability score of 7 or above, thatarm of the study will be halted immediately. If an adverse medical reaction occurs, all testing with that participant will be halted.

C. STRATEGIES TO IMPROVE ADHERENCE TO INTERVENTION PROTOCOLS, AND ANY PROCEDURES FOR MONITORING ADHERENCE

As this is a one-time (1hr) experiment, the adherence will only be monitored within the protocol of the study. Online pre-screening and consent collection ensure informed participation. Researchers will monitor participant experiences throughout testing and offer flexibility in scheduling when needed. Participants receive 10 GBP per hour or SONA credits for engagement with this study.

Experiments are run in the laboratory with a researcher present at all times; participants will be guided and monitored through the entirety of the experiment, guaranteeing the correct administration of the study protocol. All researchers follow an agreed-upon script to reduce researcher bias across the study.

D. RELEVANT CONCOMITANT CARE AND INTERVENTIONS THAT ARE PERMITTED OR PROHIBITED DURING THE TRIAL

Participants undergoing psychotropic treatment or additional talk-based therapeutic interventions are not excluded from participation in this study, but the medication or supplement and self-reported familiarity with their psychotropic treatment will be recorded.

12. PRIMARY, SECONDARY, AND OTHER OUTCOMES, INCLUDING THE SPECIFIC MEASUREMENT VARIABLE, ANALYSIS METRIC, METHOD OF AGGREGATION, AND TIME POINT FOR EACH OUTCOME; EXPLANATION OF THE CLINICAL RELEVANCE OF CHOSEN EFFICACY AND HARM OUTCOMES IS STRONGLY RECOMMENDED

Primary outcome:

- Safety outcomes: no adverse medical incidents (no medical intervention needed)
- Maximum tolerability score per 30 second section (0-10 scale)

Data from Dreamachine suggests a high safety and tolerability profile to stroboscopic stimulation in the general population. However, we need to assess if this is also th case in MDD

The safety outcomes are crucial in assessing the risks of stroboscopic light for people with MDD. If medical intervention is required due to the administration of (certain parameters) of strobe light, their administration will not be appropriate in this population.

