The tolerability score will be used to determine which parameters are appropriate for developing the WP2 intervention. Tolerability scores above 7 indicate severe discomfort due to associated side effects. Strobe light parameters that elicit a tolerability score exceeding 7 with an 80% confidence limit will be considered inappropriate for administration to the MDD population and will not be included in the intervention.

Secondary outcomes:

Secondary outcomes will only be explored through exploratory analyses between sessions and participants, and will include the following measures:

- Type, frequency and intensity of symptoms
- Feasibility, participant recruitment numbers over time
- Participants' report of arousal, enjoyment, overall discomfort and engagement as reported through single items (scale 0-100).

The type, frequency, and intensity of side effects associated with strobe light parameters will provide early insights into potential mild symptoms that strobe light may cause in individuals with MDD, serving as an early indicator for future treatments.

Feasibility does not have direct clinical implications beyond being an estimate of the local population with MDD and general interest in experiencing strobe.

Participants' arousal, enjoyment, overall discomfort and engagement do not have direct clinical implications, but will be analysed to understand trends of participants' experiences during different strobe light parameters and used to inform the development of the intervention in WP2.

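### Worsening of depressive symptoms is checked in each participant after exposure, but no WP1 outcome or analysis carries the result into the trial's safety conclusion

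*Protocol*

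**What the plan says.** Objective O1 (Protocol, section 7) is: "Evaluate the safety and tolerability of exposure to stroboscopic light in MDD".

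The description of the testing session (Protocol, item A on interventions, after section 10) gives the reason for the closing mood scales: "To ensure that the experimental procedure has not inadvertently increased participants' depressive symptoms, participants will fill out the M3VAS change and the PHQ-9 again". Support and referral follow from "any increase in M3VAS scores in the pre-to-post measurements". The destinations range from student counselling to the GP or A&E, according to severity. Section 22 places the start and end M3VAS and PHQ-9 within the adverse-event procedures and adds that the clinician co-investigator is informed. Section 30 repeats this for the M3VAS.

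Section 12 names two primary outcomes. One is the highest tolerability score in each 30-second section. The other reads: "Safety outcomes: no adverse medical incidents (no medical intervention needed". Its consequence is stated as: "If medical intervention is required due to the administration of (certain parameters) of strobe light, their administration will not be appropriate in this population".

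Section 12 introduces the secondary outcomes with: "Secondary outcomes will only be explored through exploratory analyses between sessions and participants, and will include the following measures". The list covers side-effect symptoms, recruitment numbers and 0-100 ratings of the session experience. Section 20A describes the tolerability rule and exploratory summaries of side effects and experience ratings. It mentions neither mood scale. The interventions item does say "Our primary measure of depressive symptomatology is the Patient Health Questionnaire-9 (PHQ-9", but no WP1 outcome uses it.

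**The concern.** The protocol itself identifies increased depressive symptoms as a possible harm of the procedure and collects two scales to look for it. That harm is specific to this population, and establishing safety in this population is the reason for WP1. The result is then used one participant at a time. A participant who feels worse and is directed to counselling adds nothing to the safety outcome as defined, nothing to the tolerability score, and nothing to any named secondary outcome. The plan could be followed to the letter, find no medical incidents and acceptable discomfort scores, and reach a favourable conclusion on O1 without saying how many participants left with worse mood. WP2, with 30 minutes of exposure weekly for four weeks, would be designed on that conclusion.

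**Working it through.** **Step 1. Look for a place where the mood result could be counted.**

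- *Safety outcome (section 12).* Counts medical incidents needing intervention. Medical intervention is not defined. GP or A&E referral might qualify; student counselling on its face would not.
- *Tolerability score (sections 12.1 and 12.5).* The highest discomfort rating for side effects taken from three subscales of the Visual Discomfort Questionnaire: sickness, eye and head. It has no mood item.
- *Secondary outcome on symptoms (section 12).* The explanatory text ties it to side effects of strobe parameters, which come from the same three subscales. Depressive symptoms are not among them.
- *Experience ratings (section 12).* Single items on enjoyment, engagement, arousal and discomfort. The protocol says that they lack direct clinical implications.
- *Recruitment numbers.* Not relevant.
- *Analysis (sections 20A and 20B).* No pre-to-post M3VAS or PHQ-9 summary is named.
- *Adverse events (section 22).* Both scales appear, for monitoring, referral and notification. No trial-level summary is given.

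The result is collected and acted on, but no outcome or analysis receives it.

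**Step 2. Sample size available.** Section 14 takes 25 evaluable participants and 20% dropout: 25 / (1 − 0.20) = 31.25, rounded up to 32. The plan's figure reproduces. The point does not depend on it, but 25 and 32 are the two sizes used below.

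**Step 3. Illustration of what could go uncounted.** Let p be the proportion who worsen and receive only non-medical support. The protocol gives no value, so 5%, 10% and 20% are assumptions. The chance of at least one such participant is 1 − (1 − p)^n.

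- p = 5%: 1 − 0.95^32 = 0.806; 1 − 0.95^25 = 0.723.
- p = 10%: 1 − 0.90^32 = 0.966; 1 − 0.90^25 = 0.928. Expected cases are 32 × 0.10 = 3.2 and 25 × 0.10 = 2.5.
- p = 20%: 0.999 and 0.996.

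In each case the safety outcome could still record zero. These figures show that such cases would probably be seen if the rate were in this range. They do not show that the rate is in this range.

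**Step 4. What a descriptive summary could deliver.**

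- With no events, the exact two-sided 95% upper limit is 1 − 0.025^(1/n): 10.9% for n = 32 and 13.7% for n = 25.
- With three events, the exact 95% interval is 2.0% to 25.0% (n = 32) or 2.5% to 31.2% (n = 25).
- For mean change, the 95% half-width is t(0.975, n − 1)/√n in SD units: 0.36 SD for n = 32 and 0.41 SD for n = 25.

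These limits describe the proposed table, not a fault in the plan.

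**Step 5. Which baseline.** Section 13 places the PHQ-9 and M3VAS in the online pre-trial survey, and the interventions item also puts the scales before the study. Section 22 says start and end of the experiment. The choice matters because entry requires "PHQ-9 score indicative of mild to severe depression (score of 5-27". Selecting people because a score reached 5 or more means that, on average, the next score tends to fall back. Change measured from the screening score is therefore biased toward improvement and would understate worsening.

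**The case against.** The strongest reply is that section 22 is the protocol's harms section and already covers mood: the start and end scores sit among the procedures for collecting, assessing, reporting and managing unintended effects. In addition, the secondary outcomes and exploratory analyses are introduced as open lists, so nothing prevents the investigators from reporting mood change, and detailed tabulation belongs in a SAP that is not at hand. Much of this stands. A reader might infer that mood harm is ignored or that its reporting is barred; the documents support neither. What remains is that section 22 specifies no trial-level summary, and which harms count as safety outcomes is settled in section 12, where this one is missing.

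A reader might also infer that medical intervention is the only ground on which a parameter can be judged inappropriate. That is wrong: section 12 gives a second ground, a tolerability score above 7 with an 80% confidence limit. That second ground does not help here, because the score has no mood content.

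A further reply is that no parameter choice in WP1 would change, since one end-of-visit score cannot be traced to a 30-second section, and that WP2 will measure symptoms against a control. Both facts are right. But O1 asks about safety of exposure as well as about parameters, and WP2 presents its symptom measurement as exploring therapeutic effects, after WP1's safety conclusion has been drawn.

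**Conclusion.** The point holds as a gap in trial-level reporting. Milder worsening of mood that leads to non-medical support can be left out of the WP1 safety conclusion, although the protocol collects the data to detect it. It is worth correcting but not critical, because individual safeguarding is in place and more serious worsening may already count as a medical incident.

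The size of the harm cannot be stated from the protocol. The 5% to 20% range is assumed, and the resulting probabilities (72% to over 99% of seeing at least one case) should not be read as evidence that participants will worsen. The conclusion rests on reading medical intervention as not including counselling or similar support, which the protocol leaves undefined, and on reading side-effect symptoms as those from the three questionnaire subscales, which sections 12 and 12.1 support.

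**What to change.** - **Section 12:** add pre-to-post change in M3VAS and PHQ-9 as a descriptive safety outcome. Name the start-of-visit scores described in section 22 as the baseline. Keep the online PHQ-9 in section 13 for eligibility only.
- **Section 20A:** for everyone exposed to at least one session, report the mean change with a 95% confidence interval, the number with any M3VAS increase (the existing referral trigger, which will include ordinary variation), and the number referred by type of referral.
- **Safety conclusion:** state that it considers these results alongside medical incidents, with no pass/fail rule.

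Further tabulation can be left to the SAP.

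The cost is a few sentences and one table from data already planned. If the start-of-visit scales in section 22 were in practice the online ones, two short questionnaires would be added to the visit. The table has limits that should be stated with it: estimates will be imprecise at this sample size, change cannot be attributed to the strobe without a control, and a single closing score cannot be tied to one parameter.

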Controllable parameters affecting the subjective intensity of stroboscopic experiences include luminance, stimulation frequency, rapid frequency alterations, and duty cycle. We will test each single parameter in separate stroboscopic sessions. Our aim is for the initial session to induce minimal effects, with subsequent sessions using a staircase method to gradually increase luminance, stimulation frequency, frequency transitions and duty-cycle change, corresponding to increased overall subjective intensity. While data from the Dreamachine shows a high tolerability to stroboscopic light in the general population (>40,000), it remains to be established if this is also true in people with MDD.

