8. TRIAL DESIGN

This is a single-arm safety and tolerability study (with dose escalation).

METHODS: PARTICIPANTS, INTERVENTIONS, AND OUTCOMES

9. DESCRIPTION OF STUDY SETTING AND LIST OF COUNTRIES WHERE DATA WILL BE COLLECTED

Demographic information and inclusion criteria data will be collected online via Qualtrics; participants will be excluded at this point if they are not eligible based on the outlined inclusion and exclusion criteria.

Testing will take place within the Sussex Centre for Consciousness Science's laboratory, on the University of Sussex Falmer Campus. Participants are tested within a sound-proof booth with computer equipment to record their answers using the online-survey tool Qualtrics between strobe sessions, with the strobe light being placed on the outside of the window of the booth.

All testing will take place in Brighton, England.

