Within the current study, a maximum luminance of 3800 lux over the participant's (closed) eyes at a distance of 1 meter will be used. Previous research has administered stroboscopic light successfully to influence mood states; our research expands this literature by assessing the safety and tolerability of this approach in the MDD population (Johnson et al., 2024).

Participants will undergo 11 stroboscopic sessions of increasing subjective 'intensity', following a fixed order, each lasting 2 minutes. The first 10 sessions are divided into four 30-second sections to test incremental changes in parameters; luminance, stimulation frequency, rapid frequency changes, and duty cycles. Initial sections are designed to induce minimal effects, with subsequent sections using a staircase method to gradually increase the intensity of the stroboscopic experience (see Figure 2). The final session (session 11) will contain a combination of all tested parameters.

| | 1 | 1 | |
|----------------|---------------------------|------------|---|
| Session Number | Tested Parameters | Split | Steps |
| 1 | Luminance | 4 x 30 sec | 10, 30, 50, 70 |
| 2 | Luminance | 4 x 30 sec | 70, 80, 90, 100 |
| 3 | Frequency | 4 x 30 sec | 3, 5, 7, 9 |
| 4 | Frequency | 4 x 30 sec | 9, 11, 13, 15 |
| 5 | Frequency Shift Small | 4 x 30 sec | 3, 3.75, 4.69, 5.82 (multiplicative ratio of 1.25x base Hz, a major third) |
| 6 | Frequency Shift Moderate | 4 x 30 sec | 3, 4.5, 6.75,10.13 (multiplicative ratio of 1.5x base Hz, a perfect fifth) |
| 7 | Frequency Shift Larger | 4 x 30 sec | 3, 6.6, 14.52, 6.6 (multiplicative ratio of 2.2x base Hz, close to a ninth) |
| 8 | Duty Cycle Shift Small | 4 x 30 sec | 50, 55, 60, 65 |
| 9 | Duty Cycle Shift Moderate | 4 x 30 sec | 40, 50, 60, 70 |
| 10 | Duty Cycle Shift Larger | 4 x 30 sec | 25, 50, 75, 50 |
| 11 | Dynamic sequence | 120 sec | Combination of the above parameters |

Figure 2. Individual Stroboscopic Stimulation Session Parameters for Work Package 1.

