In our study, we have established comprehensive procedures for collecting, assessing, reporting, and managing both solicited and spontaneously reported adverse events (AEs) and other unintended effects related to trial interventions or conduct. After each 2-minute strobe session, participants will be prompted to report any discomfort or side effects experienced during the session. They will rate any symptom related discomfort on a scale from 0 to 10. If a participant reports severe symptom discomfort (score >7), testing sessions involving increases of that specific parameter will be halted for that participant to prevent further discomfort, and partial data collected up to that point will be retained for analysis. Any severe adverse clinically relevant events or significant concerns will be promptly reported to the Co-Investigator, [name]. [name] has extensive experience as PI on multiple clinical trials and experimental medicine studies in patients; he has worked as a psychiatrist for 25 years, including 16 years as a consultant (with expertise in affective disorders, psychosis, and liaison psychiatry). Participants will complete the M3VAS and PHQ-9 assessments at the start and end of the experiment to monitor their well-being. If a participant's well-being deteriorates, they will be referred to appropriate mental health services, and [name] will be informed. In rare cases of psychological distress or any concerns from the researchers, [name] will be notified to determine appropriate actions. These procedures are designed to ensure participant safety and comply with regulatory requirements for adverse event reporting in clinical trials.

23. FREQUENCY AND PROCEDURES FOR AUDITING TRIAL CONDUCT, IF ANY, AND WHETHER THE PROCESS WILL BE INDEPENDENT FROM INVESTIGATORS AND THE SPONSOR

All researchers will follow a script and calibrate their conduct periodically through internal reviews.

ETHICS AND DISSEMINATION

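### A tolerability score of exactly 7 triggers the participant-level stop in 11B but not in 11A or section 22, and how session 11 is handled after a stop is ambiguous

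*Protocol*

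**What the plan says.** The stop for an individual participant appears in three places in the Protocol. (Items 11A and 11B are the lettered items A and B on interventions and discontinuation, between sections 10 and 12.)

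- **11A, interventions:** "Any report of a scorer >7 will result in that parameter's testing being stopped immediately to avoid further discomfort".
- **11B, criteria for discontinuing or modifying the intervention for a given participant:** the default is that "we will not be discontinuing the intervention unless requested to by the participant", with the exception that "if participants report a tolerability score of 7 or above, thatarm of the study will be halted immediately". All testing of a participant stops only for an adverse medical reaction.
- **Section 22, adverse events:** "If a participant reports severe symptom discomfort (score >7), testing sessions involving increases of that specific parameter will be halted for that participant".

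The scale runs from 0 to 10. 11A labels scores above 7 as severe, and section 12 repeats that cut-off.

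Section 8 describes the design: "This is a single-arm safety and tolerability study (with dose escalation"). Section 6B names the parameters: "Controllable parameters affecting the subjective intensity of stroboscopic experiences include luminance, stimulation frequency, rapid frequency alterations, and duty cycle". 11A lists the same four, and the session table assigns sessions 1-10 to them. On the last session 11A says: "The final session (session 11) will contain a combination of all tested parameters".

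**The concern.** The two thresholds give opposite instructions for the same answer. Under 11B a participant who reports 7 is stopped for that parameter. Under 11A and section 22 the same participant is not, and given the default in 11B the next session goes ahead. This is the only stop tied to a score, in a study whose primary outcome is safety and tolerability. The end-of-visit mood measures lead to support and referral, not to a halt in stimulation.

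What is halted is also worded in three ways: the testing of that parameter (11A), an arm of a study that has only one (11B), and later sessions with increases of that parameter for that participant (22). For sessions 1-10 the intention can be worked out from the four named parameters. For session 11 it cannot. That matters most after a stop in the last session of a parameter, because session 11 is then the only later session containing it.

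**Working it through.** **The plan's own figure.** The only design figure that can be recomputed is the total sample size: 25 / (1 − 0.20) = 31.25, rounded up to 32, as stated in section 14. The point does not rest on it; 32 is used below only for scale.

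**Where the rules differ.** With whole-number ratings (an assumption; the appendix only asks participants to select a number), 11B stops at {7, 8, 9, 10}, and 11A and section 22 stop at {8, 9, 10}. The difference is {7}. 11B is the outlier, since both severity definitions also use above 7. But 11B is where a researcher would look for the discontinuation criterion.

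**What depends on it for one participant.** Inputs from the session table in 11A: 11 sessions × 2 minutes = 22 minutes; sessions 1-10 × 4 sections = 40 section scores; session 11 is one undivided 120-second block. Side effects are asked after each session, so a stop can affect later sessions only. Minutes = 2 × number of later sessions of the same parameter, plus 2 if the stop reaches session 11. Frequency and frequency shift count as separate parameters, as in 6B and 11A.

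| Score of 7 in session | Later sessions of that parameter | Minutes, stop does not reach session 11 | Minutes, stop reaches session 11 | Section scores (of 40) |
|---|---|---|---|---|
| 1 | 2 | 2 | 4 | 4 |
| 2 | none | 0 | 2 | 0 |
| 3 | 4 | 2 | 4 | 4 |
| 4 | none | 0 | 2 | 0 |
| 5 | 6, 7 | 4 | 6 | 8 |
| 6 | 7 | 2 | 4 | 4 |
| 7 | none | 0 | 2 | 0 |
| 8 | 9, 10 | 4 | 6 | 8 |
| 9 | 10 | 2 | 4 | 4 |
| 10 | none | 0 | 2 | 0 |

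The range is 0-4 minutes without session 11 and 2-6 minutes with it. In four of the ten single-parameter sessions (2, 4, 7, 10), the stop prevents nothing unless it covers session 11.

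**Does any text cover session 11?** Section 22 halts later sessions that involve increases of the parameter. Session 11 combines all tested parameters, so it can be read as one of them. The default in 11B, together with its full halt only for a medical reaction, points towards giving it. Neither says whether it is omitted, altered or delivered in full.

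**How often.** The protocol gives no expected distribution of scores. If each of 32 participants had an assumed probability p of ever reporting exactly 7, the chance of at least one such report is 1 − (1 − p)^32:

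- p = 1%: 27.5% (0.3 participants expected)
- p = 3%: 62.3% (1.0)
- p = 5%: 80.6% (1.6)
- p = 10%: 96.6% (3.2)

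**Effect on the section verdict.** Section 20A calls a section tolerable if the upper 80% confidence limit is below 7. Take this as a t interval for the mean with n = 25. One score of 10 and twenty-four 0s give mean 0.40, SD 2.0, SE 0.40 and an upper limit of 0.40 + 1.318 × 0.40 = 0.93. Three 10s and twenty-two 0s give 2.07. A few high scores among zeros therefore leave the limit far below 7. This does not test the effect of section scores lost after a stop.

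**The case against.** The strongest reply is that this is an inconsistency at one value. Two of the three stop rules and both severity definitions use above 7, so the likely intent is clear and 11B could simply be corrected. Researchers follow an agreed script and calibrate periodically. A researcher is present throughout, there is a break after each session, and a participant may withdraw at any time. The word arm in 11B is loose, and nobody would read it as closing the whole study.

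Much of this stands. A reader might infer that staff will in fact treat a 7 differently; the script is not shown, so divergent practice is possible but not demonstrated. A reader might also infer that the protocol is silent on session 11, or that it is certain to be given after a stop. The documents do not support either, because the wording of section 22 can be read to include it. Nor are at least 2 minutes always at stake: that holds only if the stop reaches session 11.

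What the reply does not remove is the contradiction itself. The safeguards it lists leave the score-based rule undefined at 7, and a script must depart from either 11B or the other two sections.

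**Conclusion.** The point holds, at minor to should-fix level. At a score of exactly 7 the only score-based stop is contradictory in current text, and the handling of session 11 after any stop is ambiguous. The exposure at stake is 0-4 or 2-6 of 22 minutes per affected participant, depending on whether the stop reaches session 11, and up to 8 of 40 section scores. These counts assume the protocol's own parameter labels; a frequency stop that also reached the frequency-shift sessions would raise them. The number of participants affected is unknown.

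A reader might go on to infer that some section would be wrongly declared tolerable or intolerable. Nothing in the protocol shows that, and it is not concluded here. This is a matter of participant protection and consistent conduct, which belongs in the protocol and not in an analysis plan.

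**What to change.** 1. Use one threshold in 11A, 11B and section 22. A score of 7 or higher is the more protective choice, and no existing stop sentence forbids stopping at 7. Correcting 11B to above 7 would also remove the contradiction, but is less protective.
2. If 7 or higher is chosen, remove the word severe and its bracketed cut-off from the stop sentence in section 22 and refer only to a tolerability score of at least 7. Otherwise section 22 would call a 7 severe while 11A and section 12 do not. The severity anchor and the section verdict rule then stay unchanged.
3. Replace the reference to an arm in 11B with the scope in section 22, and align 11A with it: later sessions with increases of that parameter, for that participant.
4. State that this scope includes session 11, which is either omitted or given with that parameter held below the level that triggered the stop.
5. Carry the rule into the researcher script and the Qualtrics logic.

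The cost is wording, script and survey logic, with no extra participants. A few high-intensity section scores will be lost. Omitting session 11 loses none of the 40 section scores, but its ratings would then come only from participants without a stop, and the report should say so.
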